## 7.4 Reporting Procedures

Subjects are instructed to report adverse events at the time of occurrence via either phone or email. Adverse events may also be identified during routine communication with the subject or review of the subject's Daily Log.

The Data Safety and Monitoring Board will use the following 0 to 5 scale to grade adverse events (AE): 0 = none or event is not clinically significant, 1 = mild AE that does not require treatment, 2 = moderate AE that does require treatment, but resolves completely, 3 = severe AE (e.g. one that results in temporary inability to conduct one or more everyday activities and requires ongoing medical attention), 4 = life threatening or results in permanent inability to conduct one or more everyday activities, and 5 = death.

In the event of an AE rated ≥2 the Clinical Director will instruct the subject to obtain medical treatment from a qualified healthcare professional. If the subject becomes ill or is physically injured due to the use of the ELITONE-UUI device, she will not be responsible for the costs required to diagnose or treat such injury. The costs of diagnosis and medical care for any complication, injury, or illness caused by the study device or properly performed non-standard of care investigational procedure required by the study will be covered by Elidah, as long as the subject has followed the study protocol. The subject will not lose any of her legal rights and she does not release Elidah and the study staff from liability for mistakes or intentional misconduct by participating in the study.

## 7.5 Follow-up for Adverse Events

The Clinical Director will follow up all AE rated ≥2 until they are resolved/stable. The Clinical Director will follow procedures of the CAPA system to address the events.

#### 8. INTERVENTION DISCONTINUATION

Subjects in the study have the right to discontinue treatment at any point during the study and for any reason. If the subject chooses to discontinue, a reason for discontinuation will be recorded and every effort will be made for the subject to complete the post-study activities defined in Table 5-1.

Elidah may wish to discontinue intervention for a subject for a variety of reasons including those listed below. Effort will be made to bring the subject into study compliance prior to terminating participation.

- Purposeful improper use of the device
- Failure to treat per the assigned schedule
- A recurring adverse event or unanticipated problem.
- Failure to maintain the Daily Log for greater than 1 week

A pause on enrollment and/or treatment of active subjects may occur if Elidah discovers a serious issue with the device/treatment (see 7.3). Elidah maintains the right to discontinue the study at any point and for any reason. Stopping treatment does not pose any risk to subjects. The study may be discontinued at any time by the IRB, FDA, or other regulatory or government agency as part of their duties to ensure that research participants are protected.

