## 5.4 Protocol Schedule

The study comprises five stages: Pre-study, Baseline, Verification, Treatment, and Post-Study.

- Pre-Study –The subjects initiate pre-study activity, which includes completion of the I-QoL Questionnaire and the Pre-study Incontinence History. The subject submits the pre-study materials to Elidah (electronically or hardcopy).
- **Baseline** –Concurrently, the subjects maintain the Daily Log for 7 days to establish a baseline of the episodes/day and pads/day measures. No treatment is administered during this period. After 7 days the subjects submit the data to Elidah (electronically or hardcopy). Subjects are instructed that they should not perform baseline activity during menses or if they are ill. Note that it is acceptable to complete or return the Pre-Study materials throughout this 7 day baseline period.
- **Verification** If the 7 day Baseline shows that the subject does not qualify based on urinary incontinence episode exclusion criteria (<1/day, >5/day) then the subject will be disqualified and the device will not be sent. The subject will be notified of disqualification, or if qualified, will be sent a link for deposit payment/hold. Qualifying subjects will be randomly assigned to a treatment group and a corresponding ELITONE-UUI device will be mailed to them.
- Treatment Subjects will self-administer treatment with the ELITONE-UUI device. Subjects will treat 5x/week for six weeks. Each treatment is 20 minutes. No more than one treatment per day. See Section 6 and Table 5-1 for a detailed description of the device and treatment regimen. If subjects are ill or in menses during the 6th study week they are instructed to extend treatment for at least 5 days after menses and/or they are in good health. During the treatment weeks subjects are required to maintain their Daily Log. There is no difference in treatment requirements between the two treatment groups.
- Post-Study Upon completion of treatment subjects complete the post-study requirements, which include the I-QoL questionnaire and a post-study usability questionnaire. Subjects are requested to complete the requirements and return the study materials to Elidah within 3 days of completing treatment. There is no difference in post-study requirements between the two treatment groups.

Table 5-1: Schedule of Subject Activities/Requirements.

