#### 5.5 Adherence Assessment

Adherence to the study regimen for the active group requires completion of ≥20 of the 30 prescribed treatment sessions, as determined from review of each subject's Daily Log and the device's memory.

Further, subjects must complete the Pre-study, Baseline and Post-Study requirements to be considered compliant. If a subject does not adhere to the study requirements they will be asked to provide a reason, which will be documented in the Case Report Form (TR-1155-FORM-10). During data analysis, this information will be reviewed by the Data Safety and Monitoring Board to determine if/how the data should be adjudicated (see 10.5).

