# 9.5 Data Analyses

This is not a hypothesis driven study. Descriptive statistics will be the primary means of data analysis. Comparison between the treatment groups may be made to, in part, support Elidah's selection of a preferred configuration for eventual product commercialization. However, this case series study is not designed to allow rigorous statistical analysis between the groups.

Electrical stimulation is known to have a positive effect on both UUI, and some women have difficulty distinguishing between UUI and SUI episodes. Accordingly, in an effort accurately capture the totality any therapeutic improvement, the study's **primary outcome measure** of efficacy is a change in total urinary incontinence (UI) leaks, both SUI and UUI. Each adherent subject's Daily Log will be used to determine the average number of urinary incontinence episodes per day for the baseline and 6th week (see 5.5 regarding subject adherence). To accommodate the likelihood that some subjects will omit log data, the "weeks" referred to in the baseline and 6th week assessments refer to the first and last 5 entries in the Daily Log. The percent reduction in UI episodes is then calculated for each patient by subtracting the final week average from the baseline average, dividing the difference by the baseline average, and multiplying by 100. The percent reductions for each patient are then used to define an average (and standard deviation) reduction for each treatment group.

UI episodes per day data may additionally be reported as a responder rate. FDA guidance suggests that subjects with a percent reduction of  $\geq$ 50% be considered responders. Accordingly, the responder rate for each treatment group will be calculated by dividing the number of subjects with a reduction of  $\geq$ 50% by the total number of subjects.

**Secondary outcome measures** will similarly use descriptive statistics (e.g. mean, standard deviation) to characterize changes from baseline. Additionally, where applicable, FDA suggested response rate thresholds will be referenced. Notes on specific secondary outcome measures include:

- Change in urgency episodes with a leak UUI leak data will be analyzed in the same manner as the primary outcome measure data.

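### Section 8 lets the sponsor stop a woman who is on track to be adherent under 5.5, and the plan fixes neither her follow-up nor how her data are analysed

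*Combined protocol and SAP*

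**What the plan says.** Section 8 separates two kinds of stop. For a woman's own decision it says: "If the subject chooses to discontinue, a reason for discontinuation will be recorded and every effort will be made for the subject to complete". What she is asked to finish is the set of post-study items in Table 5-1. For the sponsor's decision it says: "Elidah may wish to discontinue intervention for a subject for a variety of reasons including those listed below". The list includes "Failure to treat per the assigned schedule" and "Failure to maintain the Daily Log for greater than 1 week". The one safeguard attached is: "Effort will be made to bring the subject into study compliance prior to terminating participation". The passage thus begins with stopping the intervention and ends with stopping participation.

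On the schedule, 5.4 says "Subjects will treat 5x/week for six weeks", and Table 5-1 shows 5 in each week. Section 1.4 gives four to five sessions a week for the same six weeks.

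On adherence, 5.5 "requires completion of ≥20 of the 30 prescribed treatment sessions", together with the pre-study, baseline and post-study requirements. It sets no condition on log gaps during treatment. The reason for non-adherence is asked of the woman and recorded, and the Data Safety and Monitoring Board decides whether and how to adjudicate the data.

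On the analysis, 9.5 computes the primary measure from adherent women. "To accommodate the likelihood that some subjects will omit log data", it defines the baseline and final weeks as the five earliest and five latest log entries.

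Study staff are unblinded (5.7) and check the digital treatment diary bi-weekly (4.5). Analysts are blinded only for the post-treatment analysis (9.3).

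**The concern.** The rule for staying in the study and the rule for being counted are not aligned. A woman can be doing well enough to be analysed and still be open to removal, and removal can itself make her non-analysable. Membership of the primary analysis set then depends partly on an unquantified sponsor decision taken during treatment, before the analyst blinding in 9.3 applies.

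The study is descriptive, so no formal error rate is at stake. What is at stake is whether the mean reduction and responder rate describe the women who were given a device. Section 9.1 names 50% as the level the sponsor anticipates will support clearance, so the make-up of two groups of 20 matters.

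**Working it through.** **The plan's own figure.** 5 sessions × 6 weeks = 30 (5.4, Table 5-1), which reproduces the 30 in 5.5.

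**Sessions.**
- Misses allowed by 5.5: 30 − 20 = 10, which is 10/30 = 33%, or two full weeks at 5 a week.
- The schedule in 1.4 gives 4 × 6 = 24 to 5 × 6 = 30 sessions. A woman treating four times a week reaches 24: inside 1.4, above the 20 in 5.5, and 30 − 24 = 6 short of 5.4.
- Section 8 gives no number, so whether she has failed to follow the schedule is left to judgement.

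**When a stop removes adherence.** Session 20 falls at 20/5 = 4 weeks at five a week, or 20/4 = 5 weeks at four a week. A stop before that point makes 5.5 unattainable. A later stop does so only if the post-study requirements are not completed.

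**Log.** Possible entries are 7 baseline days + 6 × 7 = 42 treatment days = 49. Section 9.5 needs 5 + 5 = 10. A gap of 8 days, just over the Section 8 limit, leaves 49 − 8 = 41. If it falls in mid-treatment, neither end is touched and the primary measure is unchanged. Sessions during the gap can still be counted, since 5.5 also uses the device memory.

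**Follow-up after a stop.**

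| | Woman stops | Sponsor stops |
|---|---|---|
| Reason for the stop recorded (Section 8) | yes | not stated |
| Post-study activities pursued (Section 8) | yes | not stated |
| Daily Log continued | not stated | not stated |
| Fixed analysis handling | not stated | not stated |

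**Effect on the adherent-only mean.** Take 20 women with mean reduction m. If one woman with reduction x leaves, the mean becomes (20m − x)/19 = m + (m − x)/19. As an illustration, with m = 50% and x assumed:
- x = 0%: 1000/19 = 52.6%, up 2.6 points.
- x = 50%: 950/19 = 50.0%, no change.
- x = 100%: 900/19 = 47.4%, down 2.6 points.

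The direction depends on who is stopped, which the documents do not tell us.

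**Effect on the responder rate.** Section 9.5 divides by the total number of subjects without defining it. If sponsor-stopped women are included, removal cannot raise the rate. If they are not, removing a non-responder can.

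**Where such stops would sit.** Section 5.2 expects 50–55 enrolled for 40 completers, so 10/50 = 20% to 15/55 = 27% are expected not to complete. The split by reason is not given.

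**The case against.** The strongest reply is that discretion over treatment and a counting rule for analysis serve different purposes and can coexist. Much of that stands.

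- A reader might infer that Section 8 sets a threshold of 30 out of 30. It does not: it gives no number, says only that the sponsor may wish to act, and requires an effort to restore compliance first.
- A reader might infer that the plan expressly tolerates log gaps over one week. It expressly expects omitted entries but names no gap length; the tolerance follows from the five-entry rule and from the silence of 5.5. The log also supports session counts and the detection of adverse events, so a limit on gaps has a purpose of its own.
- A reader might infer that removal automatically takes a woman out of the primary analysis. A woman stopped early can still have a calculable final value, because it comes from her latest five entries. One stopped after session 20 who completes the post-study forms can still be adherent, and the board may adjudicate the rest.
- It is not shown that staff see leak counts when they decide. The log is hardcopy by default and returned at the end, an electronic form is optional, and the content of the digital diary in 4.5 is not described.

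What the reply does not answer is the gap in handling. The board has no stated rules for adjudication, and it includes the Clinical Director, who manages the study (10.5). The reason recorded under 5.5 is the woman's reason for not adhering, not the sponsor's reason for stopping her. Nothing gives sponsor-stopped women the follow-up promised to those who stop by choice.

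**Conclusion.** The point holds as a gap between Section 8 and Sections 5.5 and 9.5. A woman on track to be adherent can be stopped by the sponsor. If this happens before session 20, or without post-study forms, she drops out of the adherent-only mean unless the board decides otherwise, and the plan does not ensure that her outcome is collected.

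Its size cannot be derived. The plan gives no session-completion rates, no expected number of sponsor stops and no outcomes for such women. The shift of 2.6 points per woman rests on an assumed 50% mean, 20 women and a reduction of 0% in the woman who leaves; other values can reverse it.

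A reader might go further and conclude that the sponsor decides who is analysed, or that results will be inflated. The documents do not support either: the power is discretionary, exclusion is conditional, no passage links low benefit to missed sessions, and the responder denominator may already protect that measure. They show that selection is possible, not that it is intended. The change is still worth making, because it is cheap and removes the question.

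**What to change.** 1. Reconcile 1.4, 5.4, 5.5, 8 and 9.5 on the schedule, missed sessions and log gaps. Whether and when treatment is stopped is for the sponsor to settle.
2. Extend Section 8's follow-up to sponsor-initiated stops: record the reason, date and decision-maker, continue the Daily Log through week 6, and pursue the post-study forms.
3. State in 9.5 that a woman whom the sponsor discontinues for missed sessions or log gaps stays in the responder-rate denominator.
4. Report the mean reduction with these women included, using their available log data, beside the adherent-only mean. Making 5.5 the sole test would not be enough, since it would still exclude any woman stopped before session 20.
5. Report the number of sponsor-initiated stops by group, with reasons.

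The cost is a few sentences in Sections 8 and 9.5, some extra data collection and one additional summary. The downside is that a few women with imperfect compliance enter the results, so the figures may be slightly less favourable.

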#### 9. STATISTICAL CONSIDERATIONS

## 9.1 Sample Size and Power Analysis

The proposed case series study design is not hypothesis driven (see 2.3). It is designed to parallel the prior 20-subject ELITONE case series that investigated use in treating SUI and that was presented to FDA in support of 510(k) clearance. That study showed a 72% reduction in daily leaks and a 75% responder rate. Elidah anticipates that a ≥50% reduction in leaks/day and/or a ≥50% leaks/day responder rate will be adequate to support FDA clearance of the ELITONE-UUI device.

Several comparable studies were identified in the literature in which similar "≥50% reduction in episodes" metrics were reported. From these, sample-size calculations were performed to provide confidence that sufficient subjects would be enrolled achieve a measurable result.

• From Sand *et al*, 48% of subjects in the active group (2 treatments per day) were responders compared to 13% of subjects in a control (sham) group. Using these values in a chi-squared sample size calculation one finds that the treatment group for an RCT study needs to enroll 31 subjects.

<sup>1 Sand et al, "Pelvic floor electrical stimulation in the treatment of genuine urge incontinence: A multi-center, placebo-controlled trial", Am J Obstet Cycecol, 173(1):72-79, July 1995.

- From Richardson *et al*, 62% and 73% of subjects (1 treatment/day and 1 treatment every other day) were responders. This study makes reference to the response rate for the sham group in the Sand et al study (13%). Using the 62% and 13% values in a chi-squared sample size calculation one finds that the treatment group for an RCT study should include 16 subjects.
- From a similar, ongoing study in which Elidah is also the Investigator (WIRB-20162650), to date, 71% of subjects are responders. Conservatively estimating the control responder rate at 15% (about the average rate reported in the AHRQ meta-analysis for the control groups in studies using vaginal EMS, Table F97), using a chi-squared sample size calculation one finds that the treatment group for an RCT study needs to enroll 12 subjects.

These three analyses suggest a treatment group in the range of 12-31 subjects would be suitable for an RCT study. Taking a conservative approach, and appreciating that the proposed study is not an RCT design, Elidah will aim to enroll 20 subjects in each treatment group, for a total of 40 subjects. See 9.4 regarding interim analysis and stopping rules.

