## 1.5 Sample Size and Population

The population includes women ages 21-80 with mild-moderate urge urinary incontinence or mild-moderate mixed urinary incontinence with predominant urge symptoms. The study intends to have 20 women complete the study in each group.

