## 5.2 Number of Subjects

20 subjects per treatment group (40 total). Appreciating that some subjects who are initially enrolled will fail to complete treatment and return the study materials, it is likely that 50-55 subjects will be enrolled. See 9.1 for discussion of the sample size calculation.

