## 9.2 Randomization

Subjects are assigned to a treatment group at the time the device is shipped to the subject. Assignments are made alternating between Group 1 and 2 until enrollment is complete.

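### Section 9.1 counts 20 per group as enrolled where 1.5 and 5.2 mean completers, and 9.5 plans no interval for the estimates that 9.1 sets against 50%

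*Combined protocol and SAP*

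**What the plan says.** Three sections of the combined protocol and SAP give the size of the study.

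- Section 9.1: "Elidah will aim to enroll 20 subjects in each treatment group, for a total of 40 subjects". No loss is allowed for.
- Section 1.5: "The study intends to have 20 women complete the study in each group". No enrollment number is given.
- Section 5.2 gives 20 per group (40 in total), notes that "some subjects who are initially enrolled will fail to complete treatment and return the study materials", concludes that "it is likely that 50-55 subjects will be enrolled", and sends the reader to 9.1 for the calculation.

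Section 9.2 ties the end of assignment to enrollment: "Assignments are made alternating between Group 1 and 2 until enrollment is complete".

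On the basis for 20, section 9.1 says of the study: "It is designed to parallel the prior 20-subject ELITONE case series that investigated use in treating SUI". It also lists three active-versus-control calculations as background.

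On use of the results, 9.1 expects a mean reduction in daily leaks of at least 50%, a responder rate of at least 50%, or both, to be adequate for clearance. Section 9.5 plans a mean and standard deviation of the percent reduction per group for adherent subjects. A responder rate may be added, calculated as a simple proportion of all subjects. Neither 9.5 nor any other section plans a confidence interval, and 9.1 states no expected precision.

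**The concern.** Section 9.1 is where a reader looks for the number at which enrollment is complete, and both 5.2 and 9.2 lead there. It gives 40 enrolled, while 5.2 says that 50-55 enrolled are likely for a study of 40. A team that followed 9.1 literally would stop too early for the aim in 1.5, and both groups would be smaller than intended.

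The second issue is how the results will be read. The two estimates that 9.1 expects to support clearance are each compared with 50%, in groups of about 20. An observed value at or somewhat above 50% is then compatible with a wide range of true values. Nothing in the planned report shows that range.

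**Working it through.** **Loss implied by the plan.** No dropout rate is stated. Taking 40 completers (1.5) from 50-55 enrolled (5.2):

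- 1 − 40/50 = 20.0%
- 1 − 40/55 = 27.3%

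So 5.2 agrees with 1.5 if the 40 are completers: 40/(1 − 0.200) = 50 and 40/(1 − 0.273) = 55. This is a consistency check, not independent evidence on dropout.

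**What 40 enrolled would yield.** Applying the same loss to 9.1's number:

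- 40 × 40/50 = 32.0 completers, 16.0 per group
- 40 × 40/55 = 29.1 completers, 14.5 per group

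That is 8-11 women short of 40. It assumes that 9.1 and 5.2 count enrollment at the same point and that all the loss comes after assignment. The documents do not settle this. A candidate becomes a subject at consent (4.3), can be disqualified after the baseline week (5.4), and is assigned only when the device is shipped (9.2). If 50-55 counts consented women, part of the 20-27% is lost before assignment and the shortfall is smaller.

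**Precision of the responder rate.** The exact (Clopper-Pearson) 95% limits for x responders of n are the 2.5% quantile of Beta(x, n − x + 1) and the 97.5% quantile of Beta(x + 1, n − x).

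| Responders | Rate | Exact 95% CI |
|---|---|---|
| 10/20 | 50% | 27-73% |
| 14/20 | 70% | 46-88% |
| 15/20 | 75% | 51-91% |
| 8/16 | 50% | 25-75% |
| 7/14 | 50% | 23-77% |
| 20/40 (pooled) | 50% | 34-66% |

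**Precision of the mean percent reduction.** The half-width is t(0.975, n − 1)/√n × SD. The multiplier is 0.468 at n = 20, 0.533 at n = 16, 0.577 at n = 14 and 0.320 at n = 40. The documents give no SD, so I assume a range of 25-50 percentage points:

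- n = 20: 0.468 × 25 = 11.7 to 0.468 × 50 = 23.4 points
- n = 16: 13.3 to 26.7 points
- n = 14: 14.4 to 28.9 points
- n = 40 (pooled): 8.0 to 16.0 points

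**Which n applies.** Section 9.5 takes adherent subjects for the primary measure. Section 5.5 defines adherence as at least 20 of 30 sessions plus the pre-study, baseline and post-study requirements. The responder rate in 9.5 is divided by the total number of subjects. The two need not be the same. For illustration, if 50 women were assigned (25 per group) and 20 in a group were adherent with 10 responders, the rate would be 10/20 = 50% on one denominator and 10/25 = 40% on the other. The intervals for n = 20 describe the reported rate only if its denominator is 20.

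**The case against.** The strongest reply is that the enrollment conflict is loose wording that the documents largely settle. Sections 1.5 and 5.2 make the intent clear, and harm follows only if staff stop at 40 despite the forecast in 5.2. That is a fair account of the intent. It does not remove the need to correct 9.1, because 5.2 refers to 9.1 as its source.

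A reader might go further and conclude that the study will end with 14-16 women per group. The documents do not support that. The figure depends on assignment stopping at 40 and on all loss following assignment, and 'enrolled' is not defined closely enough to establish either.

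On precision, the study is declared descriptive and not hypothesis driven. A reader given the SD, the counts and n could also compute the intervals. Both points are true, so the uncertainty is not irrecoverable. But an interval is itself descriptive, and the responder rate is only optional in 9.5. It would be a further step to infer that the lower limit must exceed 50%. Nothing in the plan sets such a rule.

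A reader might also infer that the three trial-based sizes in 9.1 (31, 16 and 12) are wrong, or that 20 is unjustified because it follows the words "Taking a conservative approach, and appreciating that the proposed study is not an RCT design" yet lies below 31. Neither holds. At two-sided 5%, the pooled-variance formula with 85% power gives 29.48, 15.90 and 12.38. The unpooled formula with 90% power gives 31.11, 15.26 and 11.17. Rounded up, both come within one of the stated figures. Twenty exceeds two of the three, and the basis that fits this design, the prior 20-subject series, is already in 9.1.

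Finally, one could try to derive an SD from that series' 72% mean reduction and 75% responder rate. A normal model fitted to those figures would place about a fifth of women above a 100% reduction, which is impossible, and the series concerned stress incontinence. An assumed range is the honest course.

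**Conclusion.** The point stands in two parts. First, 9.1 is wrong as written: 20 per group is the number meant to complete, and 50-55 is the number expected to be enrolled. Stopping at 40 would cost up to 8-11 completers, under the two conditions given above, and fewer if some of the 50-55 are lost before assignment.

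Second, 9.1 relies on comparisons with 50% for which 9.5 shows no uncertainty. With 20 analysed, a 50% responder rate carries an interval about 46 points wide (27-73%). The mean is uncertain by 12-23 points either way on the assumed SD range. The size of 20 per group need not change, and the study is not invalid. This should be corrected because the sponsor intends to submit these estimates and the correction is only wording.

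**What to change.** - **9.1.** Replace the enrollment sentence with: '20 completers per group (40 in total), paralleling the prior 20-subject series; about 50-55 subjects are expected to be enrolled to achieve this.' State whether 'enrolled' is counted at consent or at device assignment. Add: 'With 20 analysed, the exact 95% CI of a responder rate is 27-73% at 10/20 and 51-91% at 15/20, and the 95% CI of the mean percent reduction is the mean ± 0.47 SD; intervals are wider if fewer are analysed.'
- **9.2.** Continue assignment until the number in 9.1 is reached, on the count that 9.1 adopts.
- **9.5.** Report the mean percent reduction with its 95% CI and each responder rate with its exact 95% CI, per group and for any pooled data, with the number analysed. Name one denominator for the responder rate, reconciling the adherent subjects used for the primary measure with the total used for the rate.

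Add no test and no pass/fail rule. Sections 1.5 and 5.2 can stay as they are. The cost is a few sentences and one interval beside each estimate, with no women beyond the 50-55 already forecast. The drawback for the sponsor is a less favourable statement of precision.
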